Women who will undergo IVF followed by PGT-A at the Reproductive Medicine Clinic of IVI RMA Lisboa will be screened each day by a study collaborator and treating physician. Eligible women will be invited to participate in the study and provided written patient information on the trial (pre-screening visit). Those who accept to participate will be requested to sign written informed consent (screening/inclusion visit).

The on-study period is planned to have an overall duration of approximately 4 weeks with 2 visits for each subject, as detailed in Fig 1. The on-study period starts on the day that informed consent is signed, which can occur up to the day of patient oocyte retrieval, and ends when the results of the PGT-A procedure are known. More information regarding the overall recruitment plan, exposure, monitoring and data collection are described below.

[figure not shown]

Figure 1 – overall on-study period scheme

C. Reference Population

Our target population are healthy women who will undergo a IVF followed by PGT-A. This study will evaluate embryo culture medium compositions of 50 aneuploid embryos, 50 euploid embryos, and 30 controls (no-embryo culture medium).

D. Subject Inclusion/exclusion criteria and case-control matching

The subject inclusion and exclusion criteria are summarized in Table .

Inclusion criteria	Exclusion criteria

 Age: ≥ 18 and < 49 years old. Body Mass Index (BMI) ≥ 18.5 Kg/m² and < 30 Kg/m². Planned for IVF followed by PGT-A. Oocytes retrieval and fertilization by ICSI Six follicles over 14 mm on the day of the triggering. Signed and dated informed consent. 	
 Previous history of poor ovarian response (< 4 oocytes retrieved) with a maximal dose of ovarian stimulation (≥ 300 IU/day). Presence of a medical condition which is known to affect ART outcome (e.g. thyroid dysfunction). Current use of anti-depressants, anti-psychotics, steroids, antiepileptics or chemotherapy. Those unable to comprehend the investigational nature of the proposed study.

Table 1 – Study inclusion and exclusion criteria

E. Intervention and Follow-up

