During the study, patients are restricted to use any type of medication that may interfere with ovarian stimulation or embryology. Specifically, current use of anti-depressants, anti-psychotics, steroids, antiepileptics or chemotherapy constitute an exclusion criterion for study participation.

G. Participant withdrawal and protocol violation

Participants may withdraw from the study at any time. Eligible participants who gave adequate consent to the study and later withdraw will be replaced. Whenever a participant does not follow the planned protocol, this will be considered as a protocol violation. Given the pilot and explanatory nature of the study, these subjects will be excluded from the analysis with justification.

H. Potential advantages and financial incentives for the participating subjects

Beyond the potential clinical advantage of the study in the future, no other clinical or financial incentive will be provided for the participating subject.

I. Collection, selection, analysis and destruction of biological samples and information

BIOLOGICAL SAMPLE GATHER PROTOCOL AND OBJECTIVE OF SAMPLE COLLECTION

ECM collection

After embryo biopsy, a minimum quantity of 25 uL of embryo culture medium will be collected at Day 3 and Day 5 (or Day 6) of embryos development. Collection of the media, will be carried out by pipetting culture

media into Eppendorf tubes which will be immediately centrifugated in a mini centrifuge during 1 minute to remove cell contamination. Supernatant will be collected to a new tube with phosphate buffer, D2O and sodium azide to prevent bacterial and fungi development. Samples will be immediately anonymized, as described below, and frozen in liquid nitrogen and then stored at -20 °C at IVI RMA Lisboa. Samples will be transferred in dry ice to ITQB, which is located at [name]. [name] will be responsible for the collection and storage of samples at IVI Lisboa. This facility has a 24-hour security system in place and access to the storage area is restricted to authorized personnel only.

Selection process of case-control sibling embryo culture media

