Samples (ECM) will be collected and identified immediately using sticker labels. These labels contain a single anonymized identifying code with the following format: <STUDY CODE> <SUBJECT NUMBER> <TYPE OF SAMPLE> <SUBJECT YEAR OF BIRTH> <SAMPLE DATE>. For example, the identifying code 2004-LIS-037-SN-01-ECM_D3-1983-30042020 provides the following information:

- <STUDY CODE>: internal reference code of study (2004-LIS-037-SN)
- <SUBJECT NUMBER>: 0X
- <TYPE OF SAMPLE>: ECM_DX (X = day 3 or day 5/ day 6)
- <SUBJECT YEAR OF BIRTH>: coded as YYYY;
- <SAMPLE DATE>: date the sample was collected, coded as DDMMYYYY.

Statistical methodology

A. Data base

Data will be collected in a secure and encrypted case report form system created specifically for the study hosted on a dedicated server firewall-protected serve. The database will be rigorously defined with the variables destined to be analyzed according to the described study objectives and will have inbuilt validation procedures to ensure the correct introduction of data and avoid cases of missing information where such is not applicable. The study team collaborating in the study will be responsible for the data collection. These anonymized data will be stored for at least an additional 25 years.

In accordance with Portuguese law, all data exported for statistical analysis will be anonymized to protect the clinical and personal information of the subjects. Finally, and prior to the statistical study, an exploratory data analysis will be carried out to review the quality of the information extracted.

B. Study Variables

MAIN-OUTCOME MEASURES (DEPENDENT)

The primary outcome of this study is the assessment of different metabolic profiles between culture medium of euploid versus aneuploid embryos.

EXPOSURE VARIABLES (INDEPENDENT)

The metabolic profile of culture medium of euploid and aneuploid embryos will be compared to culture medium without embryo (control).

CONTROL VARIABLES

The following variables will be recorded during the analysis (as continuous variables, unless mentioned otherwise):

- Female subject age (in years).
- Male subject age (in years)
- Female body mass index.
- Menstrual cycle length.
- Number of preceding ART cycles.
- Duration of infertility (in years).
- Infertility diagnoses (tubal, ovulatory, endometriosis, male factor or otherwise unexplained).
- Baseline AMH.
- Baseline AFC.
- Number of follicles >11 mm on the day of ovulation triggering.

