Pathway analysis will be performed in Metaboanalyst (www.metaboanalyst.ca) to identify which metabolic pathways are affected in aneuploid embryos. Pathway Analysis combines pathway enrichment analysis with pathway topology analysis, allowing identification of the most relevant pathways involved in aneuploidy. For that, it will be used the metabolite concentrations determined previously for the aneuploid embryos and controls; and human pathway library as reference.

Work plan

The pilot study workplan of the pilot phase includes three phases (ECM collection, ECM analysis by NMR and multivariable analysis), as detailed below.

	Months									
	1	2	3	4	5	6	7	8	9	10
Phase I - ECM collection										
Phase II - ECM analysis by NMR										
Phase III - Multivariable analysis										

The responsible persons for each phase are: I- [name]; II and III – [name]

Ethical issues

A. Ethical conduct of the study

This study will be submitted for approval by the Local Ethics Committee of IVI Lisboa. For the inclusion of all patients in the study, a signed informed consent is required, which must first be approved by this Ethics Committee.

This study respects the fundamental principles of the Declaration of Helsinki, the Council of Europe Convention on Human Rights and Biomedicine, the UNESCO Universal Declaration on the Human Genome and Human Rights, as well as the requirements of Portuguese law in the field of biomedical research, the protection of personal data and bioethics.

This study will be conducted in accordance with the ethical principles that have their origins in the Declaration of Helsinki and its most recent amendments, in compliance with the approved protocol, ICH-GCP guidelines, the EU Clinical Trial Regulation, and other national law(s) or regulatory requirements applicable in the countries where the study takes place.

B. Independent ethics committee /Institutional review board

Prior to the start of the study, the investigator is responsible for ensuring that the protocol and consent form have been reviewed and approved by a relevant IEC/IRB. The IEC/IRB shall be appropriately constituted and perform its functions in accordance with ICH-GCP guidelines and local requirements as applicable.

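### The pathway analysis contrasts aneuploid media with a control that the protocol defines as no-embryo medium, so its result cannot be attributed to aneuploidy

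*Combined protocol and SAP*

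**What the plan says.** The last paragraph of Statistical methodology, D. Statistical data analysis, plans a pathway analysis in Metaboanalyst. Its purpose is "to identify which metabolic pathways are affected in aneuploid embryos". It is described as "allowing identification of the most relevant pathways involved in aneuploidy". The inputs are the "metabolite concentrations determined previously for the aneuploid embryos and controls; and human pathway library as reference".

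The protocol says explicitly what a control sample is in two places:

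- Methodology, C. Reference Population, lists the media to be evaluated as "50 aneuploid embryos, 50 euploid embryos, and 30 controls (no-embryo culture medium"). Controls are a third group, apart from the euploid one.
- Statistical methodology, B. Study Variables, under exposure variables: "The metabolic profile of culture medium of euploid and aneuploid embryos will be compared to culture medium without embryo (control").

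The same section sets the main contrast: "The primary outcome of this study is the assessment of different metabolic profiles between culture medium of euploid versus aneuploid embryos".

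**The concern.** The pathway step uses a different contrast from the one its conclusion needs. Medium in which an aneuploid embryo has grown differs from blank medium for two reasons: an embryo of any ploidy consumes and secretes metabolites, and aneuploidy may alter that pattern. Without euploid media in the analysis, the two cannot be told apart.

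Pathways of ordinary embryo metabolism could therefore be published as pathways involved in aneuploidy, even if euploid and aneuploid media were identical. The step also gives up the design's main protection against confounding, because the euploid sibling from the same patient and cycle is replaced by medium that held no embryo.

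**Working it through.** **Plan's own figure.** The plan gives no figure for the pathway step. The 40 samples per group quoted under Objectives Assessment comes from default software parameters with no stated effect size or SD, so it cannot be rebuilt, and this point does not depend on it.

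**The contrast.** For one metabolite, write the expected concentration as

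- blank: *b*
- euploid: *b + e*
- aneuploid: *b + e + a*

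where *e* is the effect of having any embryo in the medium and *a* is the extra effect of aneuploidy. Then

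- aneuploid − blank = *e + a*
- aneuploid − euploid = *a*

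The pathway analysis as written estimates *e + a*. Its stated conclusion concerns *a*. A larger sample does not remove *e*.

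**How often a shared embryo effect would be flagged.** Inputs from the documents: 50 aneuploid and 30 blank samples (Reference Population). Assumptions: *a* = 0, samples independent, two-sided 5% test, and *e* = *d* SD, with *d* varied because the documents give no value.

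P(flagged) ≈ Φ(*d* × √(50×30/80) − 1.96), where √(1500/80) = √18.75 = 4.33.

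| Assumed *d* (SD) | 4.33 × *d* − 1.96 | P(flagged) |
|---|---|---|
| 0.3 | −0.66 | 25% |
| 0.5 | 0.21 | 58% |
| 0.8 | 1.50 | 93% |
| 1.0 | 2.37 | 99% |

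**Several metabolites together.** A simulation of 2,000 runs per scenario used 25 independent metabolites (the plan expects 20 to 30), t-tests and Benjamini-Hochberg control at 5%. Euploid and aneuploid media were identical by construction. Either 5 or 10 metabolites were shifted from blank by 0.5, 1.0 or 1.5 SD in both embryo groups.

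- Aneuploid v blank (50 v 30): at least one metabolite was flagged in 63% to 100% of runs. At a 1.0 SD shift the mean number flagged was 4.96 with 5 shifted and 10.06 with 10 shifted.
- Aneuploid v euploid (50 v 50, unpaired): at least one was flagged in about 5% to 6% of runs.

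**Limits.** These are results for metabolites, not pathways. Independence is a simplification: each patient may contribute up to 3 pairs, so 50 aneuploid samples could come from as few as 17 patients (50/3 = 16.7). The documents give no within-patient correlation with which to adjust.

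**The case against.** **Controls may mean euploid siblings.** Methodology, A. Study Design, calls this a sibling case-control study, section D mentions case-control matching in its title, and section I has the heading "Selection process of case-control sibling embryo culture media". In that vocabulary the control for an aneuploid case is its euploid sibling, and the pathway paragraph would then have a wording fault and not a wrong contrast. The reading is possible but weaker: nowhere are euploid embryos defined as the controls, and both explicit definitions say no-embryo medium. On either reading the paragraph must be corrected.

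**Euploid v blank is already planned.** The exposure-variables text compares both ploidy groups with blank. That is true of the metabolic profiles, but nothing carries the euploid media into the pathway step.

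**The step is secondary.** Pathway analysis is not among the research questions or the primary outcome, and the study is described as exploratory. This stands, and it limits the importance of the point.

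**Stronger readings that the documents do not support.**

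- A reader might infer that the contrast carries no information on ploidy. It does carry some: *a* is part of *e + a*. The contrast cannot isolate it.
- A reader might set the 99% against a 5% false-positive rate. A metabolite that embryos really shift is a true difference from blank. The error lies in attributing it to aneuploidy, and 99% holds for only one assumed shift.
- A reader might infer that the human pathway library biases enrichment because only 20 to 30 metabolites are measurable. The plan names a library but specifies neither the enrichment test nor the background set, so this cannot be shown from the documents.

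**Conclusion.** The pathway paragraph is wrong as written. Under the protocol's own definition of control, it contrasts aneuploid with no-embryo medium and attributes the result to aneuploidy, and that inference does not follow at any sample size.

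The practical size depends on how far embryos shift the medium. With no ploidy effect, the probability of flagging a given shared metabolite runs from about 25% at 0.3 SD to about 99% at 1.0 SD. It rests on assumed shifts, independent samples and embryos measurably changing the medium, which the study itself presupposes.

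The damage is confined to a secondary, exploratory interpretation. A reader might infer that the study's main result is compromised. It is not: the univariate tests and the classification models for euploid versus aneuploid media do not use the pathway step.

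**What to change.** In the pathway paragraph of Statistical methodology, D:

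1. Name aneuploid versus euploid sibling media as the pathway contrast, with an analysis that respects the pairing.
2. Keep the no-embryo media for baseline correction of both ploidy groups.
3. If an embryo-versus-blank pathway analysis is kept, run it for both ploidy groups and label the output embryo metabolism, not aneuploidy.
4. Use the word control for one group only, so that it cannot be taken for the euploid sibling in one section and blank medium in another.

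The cost is a change of wording. Euploid media are already to be collected and quantified, so no further patients, samples or spectra are needed. The drawback is that the pathway results will probably look less striking once metabolism common to all embryos is removed.
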